6.5.2 Discounting

If the outcome of the model coincides with that of the study, i.e. at one year, then discounting is not required. But if the model extends beyond the outcome of the study and given the potentially relatively long time horizons being considered in these analyses, many of the costs (and benefits) will be incurred (and experienced) in future years. Using discounting, adjustments will be made to reflect this differential timing. The base-case analysis will follow Treasury recommendations for public sector projects.

6.5.3 Presentation of results and sensitivity analysis

The results of these economic analyses will be presented using cost-effectiveness acceptability curves to reflect sampling variation and uncertainties in the appropriate threshold cost-effectiveness value. Both simple and probabilistic sensitivity analyses will be used to explore the robustness of these results to plausible variations in key assumptions and variations in the analytical methods used, and to consider the broader issue of the generalisability of the results.

7. DATA ACCESS AND QUALITY ASSURANCE

7.1. In-house Data Quality Assurance

7.1.1 Monitoring and Audit

Midwifery staff performing the PO tests will be trained by the lead research midwife, who will review their skills regularly. A sample of test results inputted in the maternity units will be cross-checked at the BCTU with paper records.

7.1.2 Statistical monitoring throughout the study

Real-time reports will be available to postnatal staff indicating missing test and questionnaire data for all participants at that centre. This will be supplemented by regular reminders from the Study Office for incomplete data. The study statistician will report on recruitment, compliance and completeness of verification to the Steering Committee quarterly.

7.2. Independent Supervision of the Study

The Study Steering Committee provides independent supervision for the study, providing advice to the investigators and the Sponsor on all aspects of the study and affording protection for patients by ensuring the study is conducted according to the MRC Guidelines for Good Clinical Practice in Clinical Trials.

If the clinical co-ordinators are unable to resolve any concern satisfactorily, collaborators, and all others associated with the study, may write through the study office to the chair of the SSC, drawing attention to any concerns they may have about the possibility of distortion of clinical practice, or of particular categories of patient requiring special study, or about any other matters thought relevant.

The study shall follow and comply with the MRC Guidelines on Good Clinical Practice, although its advice in relation to test accuracy studies is limited. The Study Team has made provisional recommendations regarding the independent supervision and data monitoring of test accuracy studies as a consequence of experiences in previous studies (55). One such recommendation is that, if desirable, the independent Data Monitoring and Ethics Committee (DMEC) should be formed as a sub-committee of the Study Steering Committee (SSC). For the purposes of this study, the SSC shall convene and nominate a three member independent DMEC from within its membership, that shall not include study researchers.

7.3. Data Monitoring and Ethics Committee: determining when clear answers have emerged

If the PO test has acceptable sensitivity and specificity, using echocardiography and clinical examination as a reference, then this may become apparent before the target recruitment has been reached. The assumed prevalence of CHD may prove to be inaccurate and require a recalculation of the sample size. Alternatively, the PO test may be found to be unworkable, new evidence of the effectiveness of the test might emerge from other sources or new technologies may be introduced to the market.

To protect against this, at 3-4 months into recruitment to the study, interim analyses of major endpoints will be supplied to the DMEC along with updates on results of other related studies, and any other analyses that the DMEC may request. The DMEC will determine whether the assumptions underpinning the sample size are correct at 3-4 months after commencement of recruitment. In particular they will be asked to examine the proportion of babies showing reduced oxygen saturation by PO and those who were diagnosed by antenatal scanning. The interim analysis will also determine if the principal question on index test accuracy has been answered and will monitor adverse events. The combined SSC/ DMEC will decide if the accuracy of the tests shows both (a) “proof beyond reasonable doubt”^{*} that one particular test is definitely superior or definitely inferior in terms of a net difference in the major endpoints, and (b) evidence that might reasonably be expected to influence the patient management of many clinicians. The SSC/DMEC can then decide whether to close or modify any part of the study. Unless this happens, however, the SSC, the collaborators and all of the central administrative staff (except the statisticians who supply the confidential analyses) will remain unaware of the interim results.

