1. BACKGROUND

1.1. Clinical Context

CHD is the commonest group of congenital malformations and affects 7-8/1000 live born newborns (1;2). It contributes to 3% of all infant mortality and 46% of deaths from congenital malformations with most deaths occurring in the first year of life. A significant proportion of these children require surgery in the first year. Survival rates for infants with CHD have increased dramatically in recent years and over 80% of children born with CHD will survive to the age of 16 years; this is due largely to improvements in surgical techniques (3). Although the commonest types of CHD do not usually develop serious problems in the neonatal period, there are a number of important cardiac defects which, if undiagnosed, can present with potentially life-threatening cardiovascular collapse in the first few days of life. Although individually less common, when taken together, these lesions contribute significantly to death in infancy. As death or poorer outcome following surgery is much more likely if cardiovascular collapse occurs prior to diagnosis, timely recognition of these cardiac defects prior to collapse is vital in order to improve outcome.

Currently in the UK, all newborn babies undergo a routine screening examination, usually in the first 24 hours after birth, during which, among other things, a careful assessment of the cardiovascular system is undertaken. However, it is estimated that over 50% of babies with undiagnosed CHD failed to be picked up by routine neonatal examination. In addition, some hospitals are deferring this examination and it is then performed by the GP – sometimes up to 10 days after birth. This increases the risk of a baby with CHD presenting with acute deterioration before the screening exam has taken place. Antenatal screening for CHD in high risk pregnancies by fetal echocardiography has been developed and in experienced hands appears a useful technique (4), however a recent HTA assessment review of *routine* ultrasound screening in pregnancy concluded that detection rates for CHD were low (5). The need for an accurate, simple, non-invasive test for CHD in the early neonatal period has led a number of investigators to examine the use of PO and although results are encouraging, as we demonstrated in our systematic review (see below), there is a clear need for a larger, robust, well conducted study to confirm the value, acceptability and cost effectiveness of such a screening programme.

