2.3. Test accuracy study design

A test accuracy study is different to an effectiveness study in that randomisation of subjects is not involved. An outline of the test accuracy study is shown in Figure 2. It is designed to generate a comparison of measurements obtained by index tests with those obtained by reference standards. In this way the accuracy of index tests can be estimated. A reference standard is a test that confirms or refutes the presence or absence of disease beyond reasonable doubt. Therefore it is sometimes also known as the gold standard. PO is the index test whereas the reference standard will be the identification of CHD cases up to one year through echocardiography, databases maintained by the West Midlands congenital anomaly register (CAR), regional cardiology referral unit, regional perinatal mortality survey, hospital information departments and, if necessary, READ codes of primary care trusts.

[figure not shown]

Figure 2 Flowchart of test accuracy study of PO as a screening tool for CHD in newborns

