5.3.2.3. Assessment of parents who receive false negative results

Parents who have received false negative results will not be definitively identified until the 12 month follow-up stage of the project. So, although some may have been included in

the sample of parents receiving negative results, the main assessment of these parents will occur at that stage and no formal comparison with their immediate post-testing perceptions will be possible within the time-frame and scope of the project.

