8.2. Local Co-ordinator at each centre

Each Trust has a designated Consultant Neonatologist to act as Principal Investigator and bear responsibility for the conduct of research at their centre. Close collaboration between

^{*} Appropriate criteria of proof beyond reasonable doubt cannot be specified precisely, but a difference of at least three standard deviations in an interim analysis of a major endpoint may be needed to justify halting, or modifying, the study prematurely. If this criterion were to be adopted, it would have the practical advantage that the exact number of interim analyses would be of little importance, so no fixed schedule is proposed.

midwifery and clinical teams is particularly important in order to ensure that recruitment of babies is maximised. The responsibilities of the Principal Investigators will be to ensure that all medical and post-natal ward staff involved are well informed about the study. This will involve distributing protocols and patient information sheets to all relevant staff, displaying publicity material where it is likely to be read, and contributing to the regular newsletters. The Principal Investigators should liaise with the study administrator on logistic, data collection and administrative matters connected with the study.

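### The 3-4 month interim may close the study on accuracy before any baby has completed the one-year reference standard, so interim sensitivity and NPV are biased upward

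*Protocol*

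**What the plan says.** Timing and purpose (section 7.3): "at 3-4 months into recruitment to the study, interim analyses of major endpoints will be supplied to the DMEC". Then: "The interim analysis will also determine if the principal question on index test accuracy has been answered and will monitor adverse events". On the consequence: "The SSC/DMEC can then decide whether to close or modify any part of the study".

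The same section describes acceptable sensitivity and specificity as something that may emerge early, "using echocardiography and clinical examination as a reference". Its footnote, printed on the page with section 8.2, offers a guide: "a difference of at least three standard deviations in an interim analysis of a major endpoint may be needed to justify halting".

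The main design uses a longer standard. In section 2.3, "the reference standard will be the identification of CHD cases up to one year through echocardiography", together with the anomaly register, the cardiac referral unit, the mortality survey and hospital records. Section 2.2 verifies test positives by echocardiography and test negatives by follow-up. Section 5.3.2.3 draws the consequence: "Parents who have received false negative results will not be definitively identified until the 12 month follow-up stage of the project". Appendix E defines serious CHD by an intervention within the first year, and part of the critical category by death or surgery within 28 days.

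**The concern.** An accuracy decision is scheduled for a time when one cell of the two-by-two table is only partly filled. True positives enter quickly. False negatives enter as they declare themselves over the year, and until then they sit among the true negatives. Sensitivity and NPV are too high meanwhile, and observed prevalence is too low. Section 7.3 sets no maturity condition and no adjustment.

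The reference named in 7.3 is also shorter than that of section 2.3: it leaves out follow-up and registers. Section 1.1 estimates that "over 50% of babies with undiagnosed CHD failed to be picked up by routine neonatal examination", and section 2.2 expects the examination not to be independent of the PO result.

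At stake is the quantity the study was sized to estimate precisely. A committee following 7.3 as written could judge the question answered on an inflated sensitivity. It could also revise the sample size on an understated prevalence.

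**Working it through.** **The plan's own figure.** Section 6.1 states that 20,000 babies give 80% power to show sensitivity above 61% (true sensitivity 75%, prevalence 5 per 1000, one-sided 2.5%, exact limits). Simulating that design with 200,000 repetitions puts the value excluded with 80% power at 61.4%, which agrees after rounding. The design figures are not in question.

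**Who is in the interim.** The protocol summary gives 20,000 over 12 months. Linear accrual is assumed.
- Babies: 20,000 × 3/12 = 5,000 to 20,000 × 4/12 = 6,667.
- Oldest baby 3-4 months; mean age 1.5-2 months; share with 12 months of follow-up, 0%.
- Share past 28 days: (91.2 − 28)/91.2 = 69% at 3 months; (121.6 − 28)/121.6 = 77% at 4 months.
- Expected CHD at 5 per 1000: 25 to 33 cases, of which 19 to 25 are true positives and 6 to 8 false negatives at 75% sensitivity.

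**Size of the bias.** Let S be true sensitivity and f the share of false negatives known at the interim. True positives are taken as already counted. That is itself a simplification for serious CHD, whose status can await an intervention, although the lesion has been seen on echocardiography.

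Apparent sensitivity = S / (S + (1 − S) f). Observed prevalence = 5 × (S + (1 − S) f) per 1000.

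| f (assumed) | Apparent sensitivity, S = 75% | Apparent sensitivity, S = 61% | Observed prevalence per 1000, S = 75% |
|---|---|---|---|
| 1 | 75% | 61% | 5.0 |
| 0.75 | 0.75/0.9375 = 80.0% | 67.6% | 4.7 |
| 0.5 | 0.75/0.875 = 85.7% | 75.8% | 4.4 |
| 0.25 | 0.75/0.8125 = 92.3% | 86.2% | 4.1 |

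With half the false negatives known, a test at 61%, the value to be ruled out, shows almost the 75% assumed in the design.

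**What f might be.** The protocol does not say. As an illustration, suppose the time until a false negative is identified is exponential. With uniform entry over m months, f = 1 − (1 − exp(−λm))/(λm), where λ = ln 2/median.
- Median half a month: f = 0.76-0.82, apparent sensitivity 79-80%.
- Median one month: f = 0.58-0.66, apparent sensitivity 82-84%.
- Median three months: f = 0.28-0.35, apparent sensitivity 90-92%.

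**Other measures**, per 1,000 babies at 75% sensitivity and 99.5% specificity: TP 3.75, FN 1.25, FP 4.975, TN 990.025. True NPV = 990.025/991.275 = 99.874%. With half the false negatives still hidden it reads (990.025 + 0.625)/991.275 = 99.937%. Specificity is (990.025 + 0.625)/(995 + 0.625) = 99.50%, in effect unchanged, so it can be looked at early.

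**The three-SD guide.** The standard error of sensitivity on 25-33 cases is √(0.75 × 0.25/25) = 8.7 points to √(0.75 × 0.25/33.3) = 7.5 points. Requiring three of these makes a chance result unlikely. It does nothing about a shift of 5 to 17 points that is present in expectation.

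**The case against.** Several points on the other side are sound.

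- **Some false negatives will be known early.** Section 4.3.1 provides echocardiography for signs at clinical examination as well as for low PO, and section 4.3.2 has registers queried periodically. A reader might infer that the committee would see sensitivity near 100% whatever the truth. That requires f = 0, which these routes make implausible.
- **A comparator exists.** A reader might infer that the criterion of one test being superior has no second test to refer to. Section 5.2 speaks of more than one index test, and section 6.3 plans a paired comparison of PO with antenatal screening based on relative true- and false-positive rates. That comparison does not need the cases negative on both tests. But 7.3 also asks whether PO has acceptable sensitivity, which is an absolute quantity and does need them.
- **No numerical stopping rule is fixed.** It is tempting to compute the chance that interim sensitivity lies three SD above 61% and call it the probability of stopping. The protocol contains no such rule: 61% illustrates power in section 6.1, the three-SD figure is only something that may be needed, and a separate condition on influencing practice must also be met. A stopping probability cannot be derived.
- **Critical CHD is less exposed.** Section 2.1 makes life-threatening CHD the primary analysis. In Appendix E the critical category rests on the lesion itself or on events within 28 days, which 69-77% of interim babies have passed. This reduces the bias but does not remove it: the rest are younger and register entries can lag. Serious CHD is also within the accuracy objective of section 1.3.
- **There are safeguards.** Completeness of verification goes to the Steering Committee quarterly (section 7.1.2), and register mismatches are presented at the interim (section 4.4). Neither is tied to the accuracy decision. An understated prevalence pushes towards a larger sample, not an early stop. On 25-33 cases its sampling error (about 0.9-1.0 per 1000) is at least as large as the bias.

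**Conclusion.** The point stands. That no baby can have completed the one-year standard at 3-4 months is a matter of dates, and the direction of the bias follows from the verification scheme. With a quarter to three quarters of false negatives known, a true sensitivity of 75% is overstated by about 5 to 17 points, against the 14 points (75% versus 61%) that the full study is sized to resolve. Observed prevalence is understated by about 0.3 to 0.9 per 1000.

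These sizes rest on the assumed f, on linear accrual and on the protocol's 75% and 5 per 1000. They are smaller for critical CHD alone and negligible for specificity. The protocol itself sets the timing, purpose, reference and authority to close, so the correction belongs there.

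**What to change.** In section 7.3:

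1. State that the study will not be closed or modified on sensitivity or NPV at the 3-4 month look, and that any later decision of that kind uses only babies with complete reference-standard follow-up under section 2.3.
2. Keep the early look for recruitment, the proportion with abnormal PO, the proportion diagnosed antenatally, completeness of verification, specificity or false-positive rate, and adverse events.
3. If observed CHD prevalence enters a sample-size recalculation, treat it as a lower bound as regards ascertainment. Barring it until 12 months would in effect abolish the recalculation, since recruitment itself lasts 12 months.
4. Align the reference wording with section 2.3 by adding follow-up and registers. Keep clinical examination, which is an early route to missed cases; dropping it would make the bias worse.

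The cost is a wording amendment and the loss of an early stop on sensitivity that could not be validly used.

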2.2. Overview

[figure not shown]

Figure 1: Flow chart of study organisation

This study will assess the accuracy, effectiveness and efficiency of PO in a delayed-type cross-sectional accuracy study. First, PO will be performed soon after delivery in all cases, which will have the advantage of identifying potentially serious low oxygen saturations in a timely fashion before symptoms are apparent. Integrating PO into the assessments performed routinely by the midwife when mother and baby are transferred from the delivery suite to the post-natal ward will make this design practicable and achieve maximum recruitment. Testing will occur early but over a range of times within the first 24 hours after birth (usually within 3-6 hours) or before discharge, allowing analysis of the optimum time for PO screening. After conducting PO, we will use different reference standards for test positive and test negative cases: echocardiography for the former and follow-up for the latter.

In this design, it would be unlikely that the subsequent clinical examination could be performed independently of the PO results, as midwives would want to alert the medical staff to a low saturation. This precludes a direct comparison of PO against clinical examination, as the latter would be prone to work-up bias. This comparison will be made through decision-analytic modelling using unblinded and historical data for input and appropriate sensitivity analyses conducted.

Clearly, in the presence of a feasible and accurate CHD screening strategy, there will be a need to consider the cost-effectiveness. The cost-effectiveness of PO in combination with postnatal clinical examination will be evaluated against examination alone and examination and antenatal screening, in a model-based analysis. Two systematic reviews of the performance of antenatal screening for CHD in first trimester (4) and second trimester (19) have been performed. Data on this group will be collected as part of our study. Using directly obtained information on outcomes and costs from a large number of babies in a real-life setting, the implications of all methods of identification of CHD will be modelled, thereby improving the generalisability of the results.

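### The closure rule in section 7.3 is comparative although the primary endpoint is the accuracy of PO alone, and it asks the SSC to judge results that it withholds from the SSC

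*Protocol*

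**What the plan says.** Protocol 7.3 opens with a question about one test: whether PO has acceptable sensitivity and specificity, and whether the main question on its accuracy has been answered early. At 3-4 months, "interim analyses of major endpoints will be supplied to the DMEC".

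The rule for acting follows. "The combined SSC/ DMEC will decide if the accuracy of the tests shows both" of two things. The first is proof beyond reasonable doubt "that one particular test is definitely superior or definitely inferior in terms of a net difference in the major endpoints". The second is evidence likely to change the practice of many clinicians. The footnote to 7.3 (in the text as supplied it falls within 8.2) says the standard of proof cannot be specified exactly, but that "a difference of at least three standard deviations in an interim analysis of a major endpoint may be needed".

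On access, the same paragraph of 7.3 continues: "Unless this happens, however, the SSC, the collaborators and all of the central administrative staff" (other than the statisticians who prepare the analyses) "will remain unaware of the interim results". Section 7.2 has the SSC "nominate a three member independent DMEC from within its membership".

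On comparators, 2.2 says of clinical examination performed after PO: "This precludes a direct comparison of PO against clinical examination, as the latter would be prone to work-up bias".

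**The concern.** The rule reads as if written for a trial of one test against another, but the study's main question is how accurate one test is. PO could be clearly better than antenatal screening and still not accurate enough to adopt, or no better and still adequate. A committee applying the text would have to choose a comparator itself, and the only paired comparison that the design leaves open is a secondary one. A 20,000-baby study could then be closed or modified on a question other than its own.

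The access rule raises a separate problem. The SSC is part of the body that decides whether interim accuracy meets the criteria, but it may learn that accuracy only if the criteria are met. Followed literally, either the SSC sees the data at every look and the promised confidentiality is lost, or it decides without the data.

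**Working it through.** **1. Is there a between-test primary endpoint?** Setting the sections side by side:

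- 2.1: the primary analysis is the accuracy of PO.
- 2.3: PO is the index test, set against a reference standard.
- 5.2: the outcomes are sensitivity, specificity, predictive values and likelihood ratios. None is a difference between tests. The plural used there for index tests is loose, given 2.3.
- 6.1: success means a lower confidence limit above a fixed value.
- 2.2 and 6.3: direct comparison with clinical examination is precluded, or biased by lack of blinding.
- 6.3: comparison with antenatal screening is secondary.

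The first closure criterion therefore has no counterpart among the primary endpoints.

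**2. Do the plan's own figures confirm a one-test design?** Inputs from 6.1: true sensitivity 75%, one-sided 2.5%, exact binomial limits. With cases D ~ Bin(N, prevalence) and detected x ~ Bin(D, 0.75), power is the probability that L(x, D) exceeds the value to be ruled out, where L is the 2.5% quantile of Beta(x, D - x + 1).

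| N | Prevalence | Value ruled out | Power (6.1 states 80%) |
|---|---|---|---|
| 20,000 | 5/1000 | 61% | 82.5% |
| 20,000 | 2/1000 | 52% | 80.8% |
| 25,000 | 5/1000 | 63% | 79.7% |
| 25,000 | 2/1000 | 55% | 80.3% |
| 30,000 | 5/1000 | 64% | 80.7% |
| 30,000 | 2/1000 | 57% | 79.8% |

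In the first row, the value giving 80% is 61.4%, which rounds to the stated 61%. The plan's figures reproduce as PO against a fixed value, with no comparator.

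**3. What would the literal rule do at the look?** The front page plans 20,000 over 12 months. Assuming even accrual, 3-4 months gives 20,000 × 3/12 = 5,000 to 20,000 × 4/12 = 6,667 babies. At 5 per 1000 that is 25 to 33 cases. Take PO against antenatal screening, with PO sensitivity 75%, independent errors, and antenatal sensitivity s assumed at 30-60% because the protocol gives none. Cases found by PO only: b = D × 0.75 × (1 - s). By antenatal screening only: c = D × 0.25 × s. Expected z = (b - c)/√(b + c).

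- D = 25, s = 30%: (13.125 - 1.875)/√15 = 2.90. At s = 60%: (7.5 - 3.75)/√11.25 = 1.12.
- D = 33.3: 3.35 at s = 30% and 1.29 at s = 60%.

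Whether three SD is reached depends on the comparator, not on whether PO is accurate enough.

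**4. What would a one-test rule at three SD do?** This is an illustration using the 6.1 values, with one-sided tail 0.00135.

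- Sensitivity above 61%: needs 23 of 25 detected (limit 63.5%) or 29 of 33 (limit 62.8%). If true sensitivity is 75%, the chance is 3.2% or 5.9%.
- Specificity above 99.3%, if truly 99.5%: about 10% at 5,000 babies and 12% at 6,667.
- Both: 0.032 × 0.10 ≈ 0.3% to 0.059 × 0.12 ≈ 0.7%.

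**5. How far does late ascertainment matter?** The reference standard runs to one year (2.3), and 5.3.2.3 says false negatives are not definitively identified until the 12-month follow-up. If only half were known at the look (assumed share), apparent sensitivity would be 0.75/(0.75 + 0.25 × 0.5) = 85.7%. The chance of passing the 61% limit would rise from 3.2-5.9% to 19-36%. With a quarter known, it would be 48-72%.

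**6. Who may see what?** In 7.3 the results go to the DMEC, the combined SSC/DMEC judges the criteria, and the SSC is told only if they are met. The second step needs information that the third withholds. The front matter adds to the ambiguity by listing one joint steering and monitoring committee for interim analysis, where 7.2 separates out a three-member DMEC.

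**The case against.** The best defence is that 7.3 leaves deliberate discretion to a committee. It opens with the right one-test question, and its footnote admits that the standard of proof cannot be exact. The three-SD difference could be measured against the 6.1 values. A paired comparison with antenatal screening does exist, with McNemar's test, and 7.3 asks the DMEC to look at antenatally diagnosed babies. On access, the DMEC receives the results and could look first, opening them to the SSC only if the criteria appear met. A DMEC drawn from the SSC is a reasoned choice explained in 7.2.

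Much of this stands. These readings are workable, so a reader who infers that the rule cannot be operated at all goes too far. They are not what the text says, however: the criterion names superiority of one test, and the decision is given to the combined body.

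Three other inferences should also be resisted.

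- **That an unblinded SSC would steer test thresholds.** Section 5.1 fixes thresholds in advance, and 7.2 gives the SSC supervision and advice. The harm is lost confidentiality in a body that can close or modify the study.
- **That 61% and 99.3% are ready-made closure boundaries.** In 6.1 they are values that the study has power to exclude, not declared minimum acceptable accuracy.
- **That a one-test rule could never be met at 2 per 1000.** With 10 to 13 cases, 61% is indeed out of reach (13 of 13 gives a limit of 60.2%). But 6.1 pairs that prevalence with 52%, which 11 of 11 already exceeds (54.8%). Allowing for variation in case numbers, the chance is 1.7-4.3%.

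**Conclusion.** The point holds as a conflict between stated rules, of moderate weight. The first closure criterion does not match the primary endpoint or the sample size, and the decision and access rules contradict each other. Both conclusions rest on the text alone.

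The calculations only give scale. They assume even accrual, 75% true sensitivity and 5 per 1000 prevalence unless stated. The antenatal sensitivities and the shares of false negatives known at the look are also assumed. They show that the literal rule depends on its comparator. They also show that a one-test rule at three SD would seldom be met at 3-4 months with complete ascertainment, but could be met far too easily if late false negatives were ignored.

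**What to change.** Reword 7.3 and its footnote as follows.

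- **Criterion.** State it for PO's own sensitivity and specificity against reference values that the sponsor fixes in advance, at the three-SD stringency already chosen. Keep both directions: clearly adequate and clearly inadequate.
- **Comparator.** State that the comparison with antenatal screening is not by itself a ground for closure.
- **Ascertainment.** State that false negatives emerge up to 12 months, so interim sensitivity is biased upward and cannot alone justify closing for adequate accuracy until ascertainment is sufficient.
- **Access.** Only the three DMEC members and the reporting statisticians see interim accuracy. The DMEC judges the criterion and sends the SSC a recommendation. Results go to the SSC only if the DMEC recommends closing or modifying the study.

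The cost is wording. Sample size, testing and patient care are unchanged. The drawback is that early closure for adequate accuracy at 3-4 months becomes very unlikely.
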